National Institutes of Health National Institute of Allergy and Infectious Diseases Bethesda, Maryland 20892

Division of AIDS (DAIDS) Pharmacokinetic Statistical Analysis Plan (PK SAP)

Protocol Name: IMPAACT P1093 - Phase I/II, Multi-Center, Open-Label Pharmacokinetic, Safety, Tolerability and Antiviral Activity of Dolutegravir, a Novel Integrase Inhibitor, in Combination Regimens in HIV-1 Infected Infants, Children and Adolescents

PK SAP Version and Date: Reporting and Analysis Plan for Phase I/II, Multi-Centre, Open-Label Pharmacokinetic Activity of Dolutegravir, a Novel Integrase Inhibitor, in Combination Regimens in HIV-1 Infected Infants, Children and Adolescents, dated 08 April 2019

INTRODUCTION

The purpose of this RAP is to describe the PK analyses as outlined in the protocol only and will be used for submission of results for the Tivicay Pediatric global regulatory submissions. The tables, figures and listings of the Primary Statistical Analysis Report as well as those in this RAP will be shared with the industry sponsors and contribute to the CSR. This PK SAP covers only the intensive pharmacokinetic assessments and analyses conducted in P1093.

STUDY OBJECTIVES AND ENDPOINTS

Objectives	Endpoints
To determine DTG exposure, its variability and clinical covariates that impact DTG disposition (e.g. age, weight) using intensive and sparse sampling and population PK analysis.	C24h, AUC0-24
To evaluate the steady-state pharmacokinetics of DTG in combination with OBT in treatment-experienced and treatment-naïve HIV-1 infected infants, children and adolescents and to determine the dose of DTG that achieves the targeted C24h and AUC024 PK parameters in this population.	C ₀ , C _{min} , C _{max} , CL/F, Vz/F and t _{1/2}
To evaluate the pharmacokinetic profile of DTG when dosed by weight bands.	Subgroup analysis for primary and secondary PK endpoints by weight band

PHARMACOKINETIC STUDY DESIGN

The overall safety and PK data of the first 4 participants on a given cohort will be evaluated with respect to the safety and guidelines per protocol. If the first 4 evaluable participants of this cohort meet both sets of guidelines, then accrual will continue, and no dose adjustments will be made. If the first 4 evaluable participants of the older cohort fail either the safety or the PK guidelines in this initial test, then the starting dose will be adjusted in the appropriate direction, (upwards for inadequate PK values; downwards for safety failure), if this is feasible. Four new participants will be treated at the new dose, and an initial evaluation of safety and PK will be made on the basis of data from these participants. The evaluation will proceed as described above. In the final assessment of Stage I results, the starting dose of a fully accrued cohort (minimum of N = 10) will be evaluated on the basis of safety

and PK guidelines. Failure with respect to the safety and/or PK guidelines will result in a dose adjustment within this cohort, with the starting dose adjusted in the appropriate direction, if this is feasible. New participants will be started on the new dose and evaluations will proceed as described above. If the Protocol Team deems a given participant's PK data to be unevaluable (e.g. because of reported non-adherence or PK results that would be physiologically implausible with good adherence), that participant will be replaced for dose finding purposes (but will continue in the study and contribute to the safety analyses). Note that the participant would be replaced for evaluating safety, as well as PK, criteria, if unevaluable PK data reflect uncertainty about appropriate exposure to the study medication. Once the dose finding procedures of Stage I have been completed for each cohort, the Protocol Team will review all safety and PK data and will make final recommendations concerning the doses. These recommendations will be reviewed by the Protocol Team. The purpose of this review process will be to take account of all available information in determining whether the dose finding algorithm has converged on the best dose for further study in Stage II or whether adjustments are needed. As part of this review process, safety and PK data will be broken down on the basis of the dosing adjustments that have been made because of the inducing or inhibiting effects of the background regimens. If there is evidence that some adjustments may have been associated with undesirable PK levels or with safety concerns, these adjustments may be modified for Stage II or further data may be gathered prior to opening Stage II. Under Version 5, the Stage I data from Cohorts III-DT, IV-DT and V-DT will also be examined by weight band. If this examination suggests that the dose under evaluation is not adequate for a given weight band and should not be used for that weight band in Stage II, then a new "weight band group" will be opened to determine an adequate dose for that weight band, and this weight band group will be evaluated like an age cohort, as described above. Participants accrued to Stage II of the study will be administered the doses determined for their age cohorts, with no individual dose adjustments on the basis of PK allowed. For purposes of analysis, data from these participants will be combined with the data from the Stage I participants who have been treated at the optimal doses determined for their cohorts and who have not required individual PK determined dose adjustments, such that their total exposure to the study drug has been at the optimal dose.

ANALYSIS POPULATIONS

Population	Definition / Criteria	Analyses
		Evaluated
Intensive	All enrolled subjects who undergo intensive PK sampling,	PK
Pharmacokinetic	received at least 1 dose of DTG, where samples are	
Concentration	collected according to the intensive sampling schedule and	
	have been analyzed.	
Intensive	All subjects in the Intensive Pharmacokinetic Concentration	PK
Pharmacokinetic	Population who provide at least one evaluable PK	
Parameter	parameter and whose samples are not excluded for any	
	reason.	

Sparse	All enrolled subjects who undergo Sparse PK sampling,	PK
Pharmacokinetic	received at least 1 dose of DTG, where samples are	
Concentration	collected according to the sparse sampling schedule and	
	have been analyzed.	
Sparse	All subjects in the Sparse Pharmacokinetic Concentration	PK
Pharmacokinetic	Population who provide at least one evaluable PK	
Parameter	parameter and whose samples are not excluded for any	
	reason.	

Sparse PK analyses will be conducted separately by the sponsor and not covered in this PK SAP

Weight Band and Cohorts

The following labels for Weight Band will be used on all tabulations where the results are displayed by Weight Band, in the following order:

- 3-<6kg
- 6-<10kg
- 10-<14kg
- 14-<20kg
- 20-<25kg
- 25-<35kg
- ≥35kg
- Overall

Note, the initial cohorts were not dosed by these weight bands. In the event that subjects are not dosed according to their weight band category they will be grouped according to the weight band for the dose they received.

The following labels for Cohort will be used on all tabulations where the results are displayed by Weight Band or Age, in the following order:

U	3,
Cohort I	Adolescents ≥ 12 to <18 years of age (tablets)
Cohort IIA	Children ≥ 6 to <12 years of age (tablets)
Cohort IIB	Children ≥ 6 to <12 years of age (granules for suspension)
Cohorts III	Children ≥ 2 to < 6 years of age (granules for suspension)
Cohort III-DT	Children ≥ 2 to < 6 years of age (dispersible tablets)
Cohort IV	Children ≥ 6 months to < 2 years (granules for suspension
Cohort IV-DT	Children ≥ 6 months to < 2years of age (dispersible tablets)
Cohort V-DT	nfants ≥ 4 weeks to < 6 months (dispersible tablets)

Formulation

The following labels for Formulation will be used on all tabulations where the results are displayed by Weight Band or Age, in the following order:

Film Coated Tablets (FCT) and Dispersible Tablets (DT)

PHARMACOKINETIC ANALYSES

All concentration-time samples will be registered in the Lab Data Management System (LDMS) database. All PK samples (including intensive and population PK) will be sent to the University of Alabama (UAB) Laboratory (see the Laboratory Processing Chart). The study database will be kept up to date by close tracking of samples. As part of Stage I, the intensive PK sample assays and pharmacokinetic calculations will be performed in real-time and the results will be reported and discussed with the Protocol Team.

Steady-state pharmacokinetic parameters will be determined from plasma concentration-time profiles using non-compartmental methods (Phoenix WinNonlin 8.0, Certara, Princeton, NJ). Calculated pharmacokinetic parameters will be: area-under-the-curve (AUC₀₋₂₄), maximum plasma concentration (C_{max}), time to C_{max} (T_{max}), plasma concentration observed at end of 24 hour dosing interval (C_{24h}), plasma concentration observed immediately to dosing of 24 hour dosing interval (C_{0}), minimum plasma concentration (C_{min}), apparent clearance (CL/F), apparent volume of distribution (Vz/F), and terminal half-life ($t_{1/2}$). AUC₀₋₂₄ will be determined using the linear-log trapezoidal rule. C_{max} , T_{max} , C_{0} , C_{24h} , and C_{min} will be taken directly from the observed concentration-time data. Intensive PK sampling is conducted between days 5 and 10 after study drug initiation and over the course of approximately 24 hours. Sparse population pharmacokinetic evaluation is scheduled at Weeks 4, 12 and 24. This will be a separate analysis conducted by the sponsor and not covered in this PK SAP.

Derived Pharmacokinetic Parameters for subjects participating in the intensive studies

Pharmacokinetic parameters will be calculated by standard non-compartmental analysis according to current working practices and using the currently supported version of WinNonlin 6.3 or higher. All calculations of non-compartmental parameters will be based on actual sampling times. Pharmacokinetic parameters listed will be determined from the plasma concentration-time data, as data permits.

Parameter	Parameter Description
AUC _(0-t)	Area under the concentration-time curve (AUC) from time 0 (predose) to time of
	the last quantifiable concentration, to be calculated using the linear trapezoidal
	rule for each incremental trapezoid and the log trapezoidal rule for each
	decremental trapezoid.
AUC(0-24)	Area under the concentration-time curve (AUC) over time 0 (predose) to 24 hours
	after dose administration, to be calculated using the linear trapezoidal rule for
	each incremental trapezoid and the log trapezoidal rule for each decremental
	trapezoid.
Cmax, Cmin	The maximum observed concentration (C _{max}) at steady-state and the time of its
CO, and T _{max,}	occurrence during a dosing interval (T _{max}) will be obtained directly from the
	observed concentration-time data. The minimum observed concentration at
	steady-state (C_{min}) is obtained directly from the observed concentration-time data.

	The predose concentration at steady state (C_0) is obtained directly from the observed concentration-time data.
C ₂₄	The observed concentration at 24 hours after dose administration.
t½	Elimination half-life associated with the terminal slope of a semi logarithmic concentration-time curve (ln2), where λz stands for the apparent terminal phase elimination rate-constant. The λz will be estimated by linear regression of logarithmically transformed concentration versus time data in WinNonLin. A minimum number of three data points will be used in calculating λz . C_{max} should not be included among these data points. As a measure of evaluating the regression analysis, R-square values (square of the correlation coefficient) over 0.85 will be ideal, although lower R-square values may be acceptable, based on individual judgement: $t\frac{1}{2} = \ln 2/\lambda z$
λz	Terminal-phase rate constant.
V _d /F and	Vd is the distribution volume that is used as a conversion factor between the total
CL/F	amount of the drug in the body and the plasma concentration. The F stands for bioavailability, which is not known for each individual because it is variable between the children. The apparent clearance (CL/F) will be calculated by dividing the dose by the AUC0-12h/24h. Vd/F will be calculated by dividing CL/F by λz .

Additional parameters may be included as required.

Terminal Slope Estimation

Data permitting, the terminal slope, λ_z , of DTG will be determined from the log-linear portion of the curve and the terminal half-life ($t_{1/2}$) calculated as $0.693/\lambda_z$. The default settings for the analysis software will be used to estimate λ_z when appropriate. Appropriateness of the estimated values will be assessed by reviewing the length of sampling time relative to half-life and the goodness of fit line through the observed data (adjusted R²). If the adjusted R² was found to be less than 85% or the estimated $t_{1/2}$ was found to be relatively long compared to the sampling time, a statement highlighting that caution should be used in interpreting the $t_{1/2}$ results will be included in the report. In general, at least three consecutive time points in the terminal phase excluding T_{max} will be used for terminal half-life determination. Oftentimes, depending on the shape of the profile and limited pediatric sampling strategy, only two consecutive time points (excluding T_{max}) may be used for terminal half-life determination, which will be noted in the report. If less than two time points are available, then λ_z , $t_{1/2}$ and V_z/F will not be calculated or reported.

AUC Values

DTG AUC0-24h will be determined using the linear up-log down trapezoidal method. Pharmacokinetic analyses will be carried out using actual sampling times. AUC0-tau with tau (dosing interval) set to 24 hours will be reported as AUC0-24h since these participants are at steady-state.

Below the Level of Quantification

Concentrations for PK analyses will be used as supplied by the analytical laboratory. The lower level of quantification in the CPQA approved and validated PK assays for DTG and RPV are 5.0 ng/ml and 1.0 ng/ml, respectively. Concentration values that are below the level of quantification (BLQ) will be handled as follows for performing NCA:

- If a pre-dose concentration is below the limit of assay detection, this value will be set to zero.
- If a concentration is BLQ after dosing at time zero and before the first measurable concentration, this value will be set to zero.
- Any embedded BLQ value (BLQ value occurring between two quantifiable concentrations) will be set to missing.
- If a concentration at 24h (C_{24h}) is BLQ and λ_z is estimable, C_{24h} will be estimated. If λ_z is not estimable, then the BLQ C_{24h} will be set to zero.
- Two or more BLQ values in succession after C_{max} (for both DTG and RPV) or BLQ values at the end of
 collection interval (8h and 10h for RPV), the PK profile will be considered non-evaluable and the
 participant either repeats the PK or a new one is enrolled.

The above approach, rather than using half the limit of quantification or some other extrapolated value is the most conservative approach when assessing if overall exposure is lower than expected/acceptable in the patient population. In data listings, BLQ values will be shown as less than the quantification limit, "< [limit]" or BLQ. For summary tables, plots and figures, BLQ values will be set at 0.001 (as zero cannot be log-transformed for depiction in logarithmic plots and calculation of summary statistics such as geometric mean). If an entire concentration-time profile is BLQ, the profile will be reported separately and excluded from the PK analysis.

Profiles with Missing or Unexpected Concentrations

For profiles with a C_{24h} value higher than the prior post-dose concentration, C_{24h} may be set to the value of the pre-dose concentration (C_{0h}) for PK parameter calculations or C_{24h} will be extrapolated to 24 hours where feasible. If either the C_{0h} or C_{24h} is missing, then one may be used in substitution for the other. PK parameter summaries (tables) will use the parameters calculated with the substituted values, and this substitution will be noted in any tables and figures. The listings of concentrations, descriptive summaries of concentrations, and figures/plots should include the originally observed concentration, along with a note on how values were substituted for PK parameter calculations. If the NCA PK parameters cannot be estimated from a given participant's intensive PK samples for any reason, intensive PK sampling will be repeated (either in the same participant or in a different participant) to achieve the quota per protocol.

Presentation of Data

Graphical representations of concentration plots by sampling time will use the nominal PK sampling for summary results, and actual PK sampling time for individual results. Graphical results of PK parameters (i.e., AUC_{0-24h}, C_{max}, C_{24h} [C_{min}]) by weight band, HIV subtype and/or in comparison to historical data in adults may also be generated. Additional graphical representations may also be prepared per CMC/SMC request.

Summary Statistics

All individual concentrations for the intensive PK evaluations at week 4 and PK parameters from intensive PK assessments may include, but are not limited to, the following descriptive statistics: number of observations available, geometric mean, geometric standard deviation (geoSD), geometric coefficient of variation (geoCV), geometric 95% confidence intervals, arithmetic mean, standard deviation (SD), CV, median, interquartile range (IQR), 5th and 95th percentiles, minimum, maximum and number of BLQ samples imputed.

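### A PK profile can be replaced on the strength of its own result, and no planned AUC0-24 or C24h parameter summary is required to include it

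*SAP*

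**What the plan says.** **The judgement rule.** In the SAP's Pharmacokinetic Study Design section the replacement rule opens with "If the Protocol Team deems a given participant's PK data to be unevaluable". It gives two examples of grounds, joined by 'or': reported non-adherence, and "PK results that would be physiologically implausible with good adherence". The consequence is that "that participant will be replaced for dose finding purposes (but will continue in the study and contribute to the safety analyses"). The section then goes further: "the participant would be replaced for evaluating safety, as well as PK, criteria, if unevaluable PK data reflect uncertainty about appropriate exposure".

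**Who sees what.** Under Pharmacokinetic Analyses, Stage I assays and "pharmacokinetic calculations will be performed in real-time and the results will be reported and discussed with the Protocol Team". The team that rules on evaluability therefore has the results in hand.

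**Two fixed rules.** Under Below the Level of Quantification (BLQ), two or more successive BLQ values after Cmax make a profile non-evaluable. The participant then repeats the PK or a new one is enrolled. For a profile that is BLQ throughout, "the profile will be reported separately and excluded from the PK analysis".

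**Populations and summaries.** The Intensive PK Concentration population has no evaluability condition. The Intensive PK Parameter population requires at least one evaluable "parameter and whose samples are not excluded for any" reason. Summary Statistics provides descriptive statistics for the concentrations and for the parameters. It mentions no parameter summary with excluded profiles put back.

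**The concern.** The second ground needs no evidence beyond the PK result. The SAP gives no threshold for implausibility and asks for no corroborating adherence record. A very low profile from a child who missed doses looks the same as one from a child who took every dose but absorbed poorly or cleared quickly. Only the second kind tells us about the dose, and the rule can remove both.

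The objectives table makes AUC0-24 and C24h the targeted quantities for choosing the dose. If low profiles from adherent children leave the evaluable set, the summaries of those parameters are centred too high and spread too narrowly, and an inadequate dose is more likely to look adequate. The sets are small, so one removal counts. The first look uses 4 participants ("If the first 4 evaluable participants of this cohort meet both sets of guidelines, then accrual will continue"), a fully accrued cohort has at least 10, and a weight band needs at least 8 evaluable (protocol letter of amendment, Section B item 2, amending Section 3.1). The SAP's introduction says the results will support paediatric regulatory submissions.

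**Working it through.** The plan states no figure to reproduce. It gives no exclusion rate, no between-child variability and, in the text supplied, no numeric PK target.

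**Step 1. Where a replaced profile can still be seen.**

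| Output | Must it include a replaced or non-evaluable profile? |
|---|---|
| Dose-finding evaluation at 4 and at 10 or more participants | No: evaluable participants only, with replacements |
| AUC0-24 and C24h parameter summaries | No: samples excluded for any reason drop out of the Parameter population |
| Concentration summaries | They can: the Concentration population has no evaluability exclusion |
| All-BLQ profiles | Reported separately, outside the PK analysis |
| Final Stage I review | Covers all safety and PK data, but no table is specified |

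The gap is therefore confined to the parameter summaries.

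**Step 2. Upper illustration of the shift.** Assume lognormal exposure with log-SD s, and assume that the lowest fraction p of profiles is removed and replaced. The geometric mean is multiplied by exp[s × φ(z_p)/(1 − p)], where z_p is the p-th standard normal quantile. The factor φ(z_p)/(1 − p) is:

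- p = 5%: 0.1031/0.95 = 0.109
- p = 10%: 0.1755/0.90 = 0.195
- p = 20%: 0.2800/0.80 = 0.350

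| Assumed s | 5% removed | 10% removed | 20% removed |
|---|---|---|---|
| 0.4 | +4% | +8% | +15% |
| 0.6 | +7% | +12% | +23% |
| 0.8 | +9% | +17% | +32% |

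Example: exp(0.6 × 0.195) = exp(0.117) = 1.12.

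**Step 3. How low the modelled cut-offs are.** The cut-off as a fraction of the median is exp(−|z_p| × s).

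- p = 5% (|z_p| = 1.645): 0.52, 0.37 and 0.27 at s = 0.4, 0.6 and 0.8.
- p = 20% (|z_p| = 0.842): 0.71, 0.60 and 0.51.

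The 20% column trims values that few teams would call implausible.

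**Step 4. Chance that a removal touches a small set.** If each profile has probability p of removal, the chance of at least one among n is 1 − (1 − p)^n.

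| n | p = 5% | p = 10% | p = 20% |
|---|---|---|---|
| 4 | 18.5% | 34.4% | 59.0% |
| 8 | 33.7% | 57.0% | 83.2% |
| 10 | 40.1% | 65.1% | 89.3% |

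**Step 5. Effect on an assumed decision.** Suppose the true geometric mean is 0.8 of a lower target, the CV is 50% (s = √ln(1 + 0.5²) = 0.47), and a dose passes when the sample geometric mean reaches the target. In 200,000 simulated sets, removing the lowest 10% raises the chance of passing from 17% to 25% at n = 4 and from 7% to 15% at n = 10. At n = 10 the mildest setting run (CV 30%, 5% removed) moves from 0.8% to 1.3%. The most extreme (CV 80%, 20% removed) moves from 16% to 54%. The 0.8, the CVs, the removal fractions and the pass rule are all assumptions.

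**The case against.** Dose finding asks what exposure a dose gives when it is taken. Keeping profiles from children who missed doses would bias exposure downward and, under the SAP's own rule, push the dose up for inadequate PK. Replacement is a reasonable answer to that. This stands, and it is why replacement should stay.

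A reader might infer four stronger points that the documents do not support:

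- **That replaced children vanish from the report.** They do not, as step 1 shows. C24h is also read directly from the observed concentrations, so the 24-hour concentration summary can largely show it with these children included. AUC0-24 has no such substitute. Nor does the text say outright that a replaced child leaves the Parameter population. It only leaves that open through a general exclusion clause.
- **That the judgement rule targets low values.** It names no direction. A test framed around good adherence points mainly to low results, but that is inference. Only the two BLQ rules are low-sided by construction. They are fixed in advance, and the successive-BLQ rule lets the same child be sampled again.
- **That geometric means decide whether a dose passes.** The PK guidelines are those of the protocol, and the protocol text supplied is only a letter of amendment. The decision statistic, and any fuller definition of evaluability, may stand in the main protocol.
- **That the SAP contradicts its own claim to a conservative BLQ approach.** That claim compares its handling with substituting half the limit or another extrapolated value. It says nothing about the effect of removing whole profiles.

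The illustration can also be faulted for trimming ordinary low values and treating every removed child as adherent. Both criticisms are fair. For a given fraction removed, taking the lowest profiles gives the largest possible rise, and any truly non-adherent child among them makes the bias smaller.

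**Conclusion.** The concern holds in a limited form. Evaluability can be decided on the PK result alone, without a threshold, by a team that has seen the result, and two BLQ rules set further low profiles aside. No planned AUC0-24 or C24h parameter summary is required to show what difference this makes. The final Stage I review of all PK data softens the problem. However, it follows decisions already taken on evaluable participants, and its recommendations are reviewed by the same Protocol Team.

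The bias is conditional: it arises only if adherent children with truly low exposure are among those removed. Its size cannot be derived from the documents. The range of about 4% to 32% is an upper illustration resting on lognormal exposure, log-SDs of 0.4 to 0.8 and removal of exactly the lowest 5% to 20%. The lower end is closer to what a rule about implausible results would do. This is an inexpensive improvement that should be made. It does not show that any selected dose is wrong.

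**What to change.** Keep replacement for dose finding, and add two things to the SAP.

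1. **Results-blind adherence record.** Before concentrations are released to the Protocol Team, record for each child the judgement on adherence and dosing history. A later ruling of implausibility can then be read against it.
2. **Listing and sensitivity summary.** List every replaced or non-evaluable profile with its reason. Add a summary of AUC0-24 and C24h by cohort and weight band over every analysed intensive profile at that dose for which the parameter can be calculated, beside the planned summary. State how many profiles could not contribute, and give counts of profiles and of children where sampling was repeated. Show medians beside geometric means, because the SAP sets BLQ values to 0.001 in summary tables and one such value can dominate a geometric mean.

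If the main protocol defines evaluability more fully, the SAP should cite that definition.

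The cost is one extra table with its listing and one step in the real-time review. The all-profiles row may look less favourable and will include some non-adherent children, so it should be labelled as a sensitivity summary and not as the basis for the dose decision. No dose or clinical rule changes.

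### The SAP's rules for values below quantification are not, as a set, the most conservative: a 24-hour value reported as below 5.0 ng/mL can enter the analysis above 5.0, and the rules conflict on when and how it is used

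*SAP*

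**What the plan says.** The SAP section Below the Level of Quantification gives the lower limits of quantification (LLOQ) "for DTG and RPV are 5.0 ng/ml and 1.0 ng/ml, respectively". It then lists BLQ rules that "will be handled as follows for performing NCA":

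- Pre-dose values, and values before the first measurable concentration, become zero.
- For the 24-hour sample the SAP has two rules. The first reads: "If a concentration at 24h (C_{24h}) is BLQ and λ_z is estimable, C_{24h} will be estimated". The second covers profiles without a usable slope: "then the BLQ C_{24h} will be set to zero".
- For a value inside the profile the rule reads: "Any embedded BLQ value (BLQ value occurring between two quantifiable concentrations) will be set to missing".
- Two or more successive BLQ values after Cmax make the profile non-evaluable.

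The SAP then states that this approach "rather than using half the limit of quantification or some other extrapolated value is the most conservative approach", with the purpose of judging whether exposure is too low. The same section adds: "For summary tables, plots and figures, BLQ values will be set at 0.001". It gives no unit and explains that zero cannot be log-transformed.

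Four other places bear on the point:

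- The parameter table under Derived Pharmacokinetic Parameters defines C24 as observed and requires at least three points for λz.
- Terminal Slope Estimation generally asks for three points but allows two.
- AUC Values prescribes linear-up/log-down.
- Profiles with Missing or Unexpected Concentrations lets a C24h above the prior post-dose value be set to the pre-dose value or extrapolated. It also says that "PK parameter summaries (tables) will use the parameters calculated with the substituted values".

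**The concern.** The word conservative here is a claim about direction: low exposure should not be made to look better than it is. The SAP supports the claim by contrasting its rules with extrapolated values, yet one of those rules is an extrapolation, and nothing stops it from returning a concentration that the assay has ruled out.

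C24h and AUC0-24 are the targets for choosing the dose (SAP, Study Objectives and Endpoints). They are judged on 4 children, then on at least 10 per cohort (SAP, Pharmacokinetic Study Design), with at least 8 evaluable per weight band (Protocol letter of amendment, update to Section 3.1). In groups this small one BLQ value can move a geometric mean visibly. If the SAP leaves open which value is used, two analysts following it can report different results.

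**Working it through.** **Inputs.** From the documents: LLOQ 5.0 ng/mL, so LLOQ/2 = 2.5; the BLQ rules; linear-up/log-down AUC; group sizes 4, 8 and 10. Assumed, because the documents do not give them: sampling at 0, 1, 2, 4, 8, 12 and 24 h, and every concentration below (ng/mL; AUC in ng·h/mL). The SAP states no figure of its own to reproduce.

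**1. When the estimate exceeds the LLOQ.** Estimate = C12 × exp(−λz × 12). It exceeds 5.0 when half-life > 12 × ln 2 / ln(C12/5).

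- C12 = 20: 6.0 h
- C12 = 100: 2.8 h
- C12 = 500: 1.8 h

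It falls below LLOQ/2 at C12 = 100 when half-life < 12 × ln 2 / ln(40) = 2.25 h. The direction is therefore conditional.

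**2. One worked profile.** Concentrations 0/400/600/400/200/100/BLQ. The values at 4, 8 and 12 h halve every 4 h, so the estimate is 100/8 = 12.5. The area to 12 h is 200 + 500 + 986.5 + 1154.2 + 577.1 = 3417.8. The last step is (100 − x) × 12 / ln(100/x):

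| C24h used | Last step | AUC0-24 |
|---|---|---|
| 12.5 (estimate) | 504.9 | 3923 |
| 5.0 (LLOQ) | 380.5 | 3798 |
| 2.5 (LLOQ/2) | 317.2 | 3735 |

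The uncapped estimate is 3.3% above the LLOQ result and 5.0% above the LLOQ/2 result. On the geometric mean of C24h, using 12.5 instead of a capped 5.0 for one child multiplies the result by (12.5/5)^(1/n): 1.26 for n = 4, 1.12 for n = 8 and 1.10 for n = 10, whatever the other children's values.

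**3. Two points or three.** Take 0/200/400/600/200/100/BLQ, with Cmax at 4 h. Only 8 and 12 h are usable for λz. Terminal Slope Estimation permits C24h = 100/8 = 12.5. The parameter table's minimum of three makes λz not estimable, and C24h becomes 0.

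**4. Embedded values.** Both neighbours are at or above 5.0, so the bridge between them never falls below 5.0. Entering 5.0 or 2.5 at the middle time lowers the area, unless all three values equal 5.0. Example 0/400/600/300/20/BLQ/6: AUC0-24 is 2165 with the 12 h value missing, 2088 with LLOQ and 2064 with LLOQ/2 (+4.9%).

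Here C24h = 6 is above a prior sample reported as below 5, so the rule for a C24h above the prior concentration may apply. Extrapolating from 4 and 8 h (half-life 4 × ln 2 / ln 15 = 1.02 h) gives C24h = 0.0004, and AUC0-24 becomes 2009 (missing), 2029 (LLOQ) and 2016 (LLOQ/2). The direction reverses. With C24h set to the pre-dose zero and an assumed linear last step, missing is again higher (2139 against 2028 with LLOQ/2). The SAP does not say whether the embedded value is removed before that comparison is made.

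**5. Which C24h is summarised.** The BLQ list gives an estimate or zero for NCA; the later sentence gives 0.001 for summary tables. C24h is both a concentration and a parameter. For one such child, 12.5 against 0.001 (read as ng/mL) changes the geometric mean by 12,500^(1/n): 10.6-fold for n = 4, 3.3-fold for n = 8 and 2.6-fold for n = 10. If 0.001 means µg/mL, that is 1 ng/mL, and the factors are 12.5^(1/n) = 1.88, 1.37 and 1.29.

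**The case against.** Much of the other side's case stands. Several rules do work downward: the pre-dose and early zeros, and 0.001. The profiles above are invented, and the documents do not say how often a dolutegravir C24h is BLQ. The team may replace a child whose results are implausible with good adherence, BLQ values are flagged in listings, and the number imputed may be reported. These points limit the practical size. They do not make an estimate above the LLOQ consistent with the assay result, or settle the conflicts between sections.

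A reader might infer more than the documents support:

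- **That embedded values always inflate AUC.** Step 4 shows a reversal once the rule on a C24h above the prior value is applied. A low value between two much higher ones may also be a faulty sample, for which missing is reasonable.
- **That a zero C24h inflates AUC.** The log step is undefined at zero, but the sign depends on an assumed linear fallback and reverses when the preceding value is low. Repeat sampling is also required when NCA parameters cannot be estimated.
- **That calling profiles with successive BLQ values non-evaluable contradicts the claim.** The SAP's sentence compares ways of assigning values, not evaluability, and the same child may repeat sampling.
- **That the large factors in step 5 show upward bias.** They arise because 0.001 is so low. The SAP justifies 0.001 as a stand-in for zero, so the natural reading is that it does not displace a non-zero estimate. What is missing is a sentence saying so: the one on substituted values sits under the next heading, for missing or unexpected concentrations.

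**Conclusion.** The concern holds in limited form. The rules as a set are not the most conservative available. An uncapped extrapolation can assign a BLQ C24h a value above 5.0 ng/mL, and the SAP contrasts its approach with exactly this kind of value. Under the assumed profile the effect on AUC0-24 is 3.3% against the LLOQ and 5.0% against LLOQ/2. With short half-lives the estimate falls below LLOQ/2, so no general upward bias is shown. The embedded rule raises AUC when the neighbours are kept as observed, and not otherwise with certainty.

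Two textual conflicts do not depend on assumed concentrations: three points against two for λz, and an NCA value against 0.001 in the C24h summary. Their numerical size does. The effect on a dose decision cannot be quantified, because the supplied text gives neither the BLQ rate nor the PK limits. The point is worth correcting because the repair is cheap and the parameters affected are the dose-finding targets.

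**What to change.** In the SAP:

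1. Cap an estimated BLQ C24h at the LLOQ.
2. Give one minimum number of points for λz, the same in the parameter table and in Terminal Slope Estimation.
3. State that the NCA value enters the C24h parameter summary, and that 0.001, with its unit, only replaces zeros.
4. Add one sensitivity analysis with embedded and terminal BLQ values at LLOQ/2, for both C24h and AUC0-24. Say whether the embedded rule is applied before C24h is compared with the prior concentration.
5. Limit the most-conservative statement to the rules for which it is true, or remove it.

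The cost is a few sentences and one small table. Summaries may come out slightly lower.
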